Nothing herein is to be disclosed in any way without the prior express
permission of W. L. Gore & Associates, Inc.

**Post-Approval Study of the GORE® VIABAHN® Endoprosthesis for the Treatment of
In-Stent Restenosis in the Superficial Femoral Artery**

Protocol Number: ISR 14-04

Protocol Date: December 10, 2015 (Revision 2)
April 10, 2015 (Original, Revision 1)

NCT Number: NCT02542267

W. L. Gore and Associates, Inc.
Medical Products Division

Nothing herein is to be disclosed in any way without the prior
express written permission of W. L. Gore & Associates, Inc.

Post-Approval Study of the GORE® VIABAHN® Endoprosthesis for the Treatment of
In-Stent Restenosis in the Superficial Femoral Artery

Protocol Number: ISR 14-04

Amendment 1 (Rev. 2)

W. L. Gore & Associates, Inc.
Medical Products Division

PROTOCOL SUMMARY

Study Title	Post-Approval Study of the GORE® VIABAHN® Endoprosthesis for Treatment of In-Stent Restenosis in the Superficial Femoral Artery
Protocol Number	ISR 14-04
IDE or PMA Number	Post approval w/PMA# P040037 S060
Sponsor	W. L. Gore & Associates, Inc. Medical Products Division [name] [contact]
Study Device	The GORE® VIABAHN® Endoprosthesis with Heparin Bioactive Surface (US); GORE® VIABAHN® Endoprosthesis with PROPATENT™ Bioactive Surface (EU); and subsequently referred to as GORE® VIABAHN® Endoprosthesis throughout this protocol.
Study Design	Prospective, multicenter, single-arm study
Study Objective	The objective is to evaluate post-market safety and effectiveness of GORE® VIABAHN® Endoprosthesis for treatment of In-Stent Restenosis of the SFA
Primary Endpoints	
Effectiveness Endpoint: Primary Patency at 12 months by Kaplan-Meier analysis
 
Safety Endpoint: Device- and procedure-related Serious Adverse Events within 30 days of the procedure

Secondary Endpoint(s)	
 • Acute Procedural Success • Primary Patency at 30 days, 12, 24, & 36 months • Primary Assisted Patency at 30 days, 12, 24, & 36 months • Secondary Patency at 30 days, 12, 24, & 36 months • Freedom from TLR at 30 days, 12, 24, & 36 months • Freedom from Major Amputation at 30 days, 12, 24, & 36 months • Change in Ankle-Brachial Index from pre-procedure at 30 days, 12, 24, & 36 months • Change in Rutherford Category from pre-procedure at 30 days, 12, 24, & 36 months • Stent Fracture Assessment at 12, 24, & 36 months
Subject Population	The Subject population will include symptomatic PAD patients (Rutherford 2-5) with occlusive lesion(s) within and adjacent to previously implanted non-covered stent(s) located in the superficial femoral artery
Number of Subjects	108 (minimum 81 (75%) of Subjects in the US) A minimum of 20 Subjects will be enrolled with a lesion length of 230-270 mm.
Number of Sites	A minimum of 15 Sites in the U.S. Up to 5 OUS Sites may be included.
Expected Time to Complete Enrollment	24 months

CONFIDENTIAL INFORMATION

MD133246 Protocol Template

Revision#: 2

Doc Type: GC

Schedule of Events	Screening: Informed Consent, Medical History, Demographics Treatment: Angiographic confirmation of final eligibility, Deployment of study device, Post-procedural angiography, Adverse Events Follow-up Schedule: 30 days, 12, 24 and 36 months Follow-up Assessments: Adverse events, ABI, Rutherford, X-ray (12, 24, 36 months), Duplex ultrasound
Expected Study Timeline	Study Initiation: SEP 2015 Number of sites with IRB approvals/month: 2 Number of subjects enrolled/month: 0.5/site Enrollment Completion: SEP 2017 Study Follow-Up Completion: SEP 2020 Final Report Submission: Submitted within 3 months of completion of the last patient follow-up

LIST OF ABBREVIATIONS

ABI	Ankle-Brachial Index
AE	Adverse Event
CAD	Coronary Artery Disease
CBC	Complete Blood Count
CDMS	Clinical Data Management System
CE	Conformité Européenne
CEC	Clinical Events Committee
CFR	Code of Federal Regulations
cm	Centimeters
CRF	Case Report Form
CRO	Contract Research Organization
ePTFE	Expanded Polytetrafluoroethylene
EU	European Union
FDA	Food and Drug Administration (United States)
Fr	French (sizing)
GCP	Good Clinical Practice
HCG	Human Chorionic Gonadotropin
HIT	Heparin-Induced Thrombocytopenia
ICF	Informed Consent Form
IDE	Investigational Device Exemption
IFU	Instructions for Use
IRB	Institutional Review Board (U.S.)
ISR	In-stent Restenosis
mm	Millimeters
OUS	Outside the United States
PAD	Peripheral Artery Disease
PI	Principal Investigator
PMA	Premarket Approval
PSV	Peak Systolic Velocity
PSVR	Peak Systolic Velocity Ratio
PTA	Percutaneous Transluminal Angioplasty
SAE	Serious Adverse Event
SFA	Superficial Femoral Artery
TBI	Toe-brachial Index
TLR	Target Lesion Revascularization
TVR	Target Vessel Revascularization
U.S.	United States

CONFIDENTIAL INFORMATION

MD133246 Protocol Template

Revision#: 2

Doc Type: GC

PROTOCOL SUMMARY	iii
1. Introduction.....	1
1.1. Disease.....	1

1.1. Disease

Patients with lifestyle-limiting claudication from atherosclerotic stenosis and occlusion of the Superficial Femoral Artery (SFA) exhibit a decreased quality of life, e.g. pain or cramping in the legs or buttocks upon exertion¹. Vascular surgeons have traditionally managed claudication conservatively, given the morbidity and mortality associated with surgical bypass procedures². If indicated, interventional techniques and devices provide clinicians with a less invasive alternative to surgery for the treatment of claudication and limb ischemia³.

Plain Old Balloon Angioplasty (POBA) of the SFA in longer lesion lengths (>10cm) has yielded reported primary patency rates of 22%⁴. Bare metal stents (BMS) have demonstrated better primary patency rates when compared to POBA alone⁵. Still, one-year restenosis rates remain high and continue to plague both therapies (PTA 64% vs BMS 37%)⁶.

Similar to coronary stenting, the leading cause of in-stent restenosis (ISR) has been identified as neointimal formation. Implant-induced hyperplasia, endothelial denudation, thrombus reorganization and negative arterial remodeling are factors that contribute to ISR. Characteristics of the originally treated lesion have been shown to predict future occurrence of ISR. Long, diffuse stenotic or occluded lesions treated with BMS commonly become restenotic^{7, 8, 9}.

1.2. Historical Treatments

The following treatment modalities have been used globally to treat in-stent restenosis of the superficial femoral artery:

- Conventional percutaneous transluminal angioplasty
- Cutting balloon
- Cryoplasty
- Atherectomy
- Re-stenting
- Drug covered balloons
- Drug-eluting stents

The GORE® VIABAHN® Endoprosthesis has been utilized as a treatment option for SFA ISR. The flexibility of the VIABAHN® Endoprosthesis, as exemplified by its low rate of fracture in long lesion lengths, allows it to withstand the mechanical forces of the SFA¹⁰. Additionally, the ePTFE can provide a physical barrier between the arterial lumen and in-growth from neointimal formation. Since this has been hypothesized to be the failure mechanism of the original stent, it would stand to reason that blocking further neointimal ingrowth via an ePTFE covering would provide a promising treatment strategy.

CONFIDENTIAL INFORMATION

[figure not shown]
[figure not shown]
MD133246 Protocol Template

Revision#: 1

Doc Type: GC

1.3. Study Device Description

The GORE® VIABAHN® Endoprosthesis with Heparin Bioactive Surface (marketed as GORE® VIABAHN® Endoprosthesis with PROPATENT™ Bioactive Surface in the EU) is a flexible, self-expanding endoluminal endoprosthesis consisting of two components: 1) a tubular section of ePTFE which has been modified with Heparin Bioactive Surface and 2) an external supporting structure, constructed from nitinol, extending along its entire length.

CONFIDENTIAL INFORMATION

MD133246 Protocol Template

Revision#: 1

Doc Type: GC

Table 1: GORE® VIABAHN® Endoprosthesis Configurations and Vessel Sizing Guidelines

Device Sizing		Introducer Sheath Size (Fr)	Introducer Sheath Size (Fr)	Available Device Lengths ¹ (cm)	Recommended Balloon Diameter for Device Touch-up (mm)
Labeled Device Diameter (mm)	Recommended Vessel Diameter (mm)	Guidewire Diameter 0.035" (0.889 mm)	Guidewire Diameter 0.018" (0.460 mm)		
5	4.0 – 4.7	7	6	2.5, 5, 10, 15, 25	5.0
6	4.8 – 5.5	7	6	2.5, 5, 10, 15, 25	6.0
7	5.6 – 6.5	8	7	2.5, 5, 10, 15, 25	7.0

¹Labeled device lengths are nominal.

The U.S. regulatory history for the GORE® VIABAHN® Endoprosthesis is as follows:

The original PMA P040037, GORE® VIABAHN® Endoprosthesis, was approved on June 14, 2005 for improving blood flow in patients with symptomatic peripheral arterial disease in superficial femoral artery lesions with reference vessel diameters ranging from 4.8 to 7.5 mm.

PMA supplement P040037/S003 was approved on April 24, 2007 to add 5mm diameter device configurations and to make associated modifications to the indications to add reference vessel diameters from 4.0 – 4.7mm.

PMA supplement P040037/S004 (GORE® VIABAHN® Endoprosthesis with Heparin Bioactive Surface) was approved on July 31, 2007 to add device configurations containing a Heparin Bioactive Surface.

PMA supplement P040037/S007 was approved on August 14, 2008 for the addition of an indication for treatment of iliac artery lesions.

PMA supplement P040037/S050 was approved on October 18, 2013 for the addition of a 25cm length for the 5-8mm diameter endoprostheses and where the indication statement was modified to specify lesion lengths.

PMA P130006 was approved on December 5, 2013 for the addition of an indication to treat stenosis or thrombotic occlusion in AV access grafts.

PMA supplement P040037/S060 was approved on September 19, 2014 for an addition of the indication to treat SFA in-stent restenosis.

Currently, the GORE® VIABAHN® Endoprosthesis is approved for the following indications in the US:

The GORE® VIABAHN® Endoprosthesis is indicated for improving blood flow in patients with symptomatic peripheral arterial disease in superficial femoral artery de novo and restenotic lesions up to 270 mm in length with reference vessel diameters ranging from 4.0 – 7.5 mm.

The GORE® VIABAHN® Endoprosthesis is indicated for improving blood flow in patients with symptomatic peripheral arterial disease in superficial femoral artery in-stent restenotic lesions up to 270 mm in length with reference vessel diameters ranging from 4.0 – 6.5 mm.

The GORE® VIABAHN® Endoprosthesis is indicated for improving blood flow in patients with symptomatic peripheral arterial disease in iliac artery lesions up to 80 mm in length with reference vessel diameters ranging from 4.0 – 12 mm.

The GORE® VIABAHN® Endoprosthesis is also indicated for the treatment of stenosis or thrombotic occlusion at the venous anastomosis of synthetic arteriovenous (AV) access grafts.

[REDACTED]							
[REDACTED]							
[REDACTED]							
[REDACTED]							
[REDACTED]							
[REDACTED]							
[REDACTED]							

[REDACTED]

[REDACTED]

[REDACTED]

2. Study Objectives

2.1. Primary Objective(s)

The primary objective of ISR 14-04 is to evaluate the post-market performance of GORE® VIABAHN® Endoprosthesis for the treatment of in-stent restenosis of the superficial femoral artery in a primarily U.S. population (at least 75% of patients being treated in the U.S.).

3. Study Design

3.1. Description of Study Design

This study is a prospective, multicenter, non-randomized single-arm study to evaluate the post-market performance of the GORE® VIABAHN® Endoprosthesis for the treatment of in-stent restenosis in the superficial femoral artery.

A minimum of 15 Clinical Investigative Sites (referred to as “Sites” in the remainder of this document) in the U.S. and a maximum of 5 OUS Sites will participate in this study.

A total of 108 Subjects (a minimum of 81 Subjects from the U.S. and a maximum of 27 OUS Subjects) will be enrolled in this study with a limit of 30 Subjects per U.S. Site.

A minimum of 20 Subjects (out of the total 108 Subjects) will be enrolled with lesion lengths of 230-270mm. The study will be actively monitored to ensure the minimum enrollment threshold for this long lesion length cohort is met.

The anticipated accrual period is 24 months assuming an accrual rate is approximately 0.5 Subjects per month/Site.

Patients are to be enrolled into the study provided all inclusion and no exclusion criteria are met as specified in Section 4. Subjects will be evaluated through hospital discharge and will be scheduled for follow-up visits at 30 days and at 12, 24 and 36 months post treatment. Accounting for the expected period of enrollment, the total estimated duration of the study is 60 months.

3.2. Study Endpoint(s)

3.2.1. Definitions

Ankle Brachial Index: the ankle systolic pressure in the study limb divided by the highest brachial systolic pressure in either arm

Acute Procedural Success: successful delivery of study device and complete coverage of the target lesion without a procedure or device-related Serious Adverse Event prior to hospital discharge

Major Amputation: removal of the lower limb above the metatarsals in the study limb, resulting from a vascular event

Patency: blood flow through the study device

Primary Patency: patent blood flow through the study device, which requires either a PSVR measurement ≤ 2.5 or patent flow indicated by the Core Lab, and without repeat intervention

Primary Assisted Patency: blood flow through the study device regardless of repeat interventions to maintain patency prior to occlusion

CONFIDENTIAL INFORMATION

MD133246 Protocol Template

Revision#: 1

Doc Type: GC

Secondary Patency: blood flow through the study device regardless of repeat interventions to maintain or restore patency after occlusion

Target Lesion(s): stenotic or occluded segment(s) within and adjacent to a previously implanted non-covered stent(s) (>30 days) in the superficial femoral artery. An adjacent lesion is an extension of the stenotic or occluded segment that is contiguous with that lesion within the previously implanted non-covered stent

Target Lesion Revascularization (TLR): repeat intervention within the study device and 5 mm proximal or distal to the edge of the study device to maintain or re-establish patency

Toe Brachial Index: the toe systolic pressure in the study limb divided by the highest brachial systolic pressure in either arm

Stent Integrity: freedom from study device stent fracture which is clearly distinguishable on imaging from the previously implanted non-covered stent

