3.2.2. Primary Endpoints

The primary effectiveness endpoint is Primary Patency at 12 months post-procedure. This will be estimated through 365 days along with a 95% confidence interval using Kaplan-Meier analysis.

The primary safety endpoint is procedure or device-related Serious Adverse Events within 30 days of the index procedure. The total number of events as well as the number of Subjects experiencing them will be tabulated along with a 95% confidence interval.

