5.7. Follow-Up

All Subjects are required to return to the Investigator for follow-up evaluations at 30 days, 12, 24 and 36 months after the index procedure. The schedule of events is outlined in **Table 3**.

Follow-up visits will be scheduled at appointed times after the date of index procedure. The Sponsor recognizes that Subjects may not be able to return for follow-up visits on the exact date required. Thus, a period during which each visit is allowed (window) is presented in **Table 4**.

Table 4 Study Visit Windows

Follow-up Visit	Window
30 days	30 ± 7 days
12 months	365 ± 45 days
24 months	730 ± 45 days
36 months	1095 ± 45 days

The following data are required and will be collected at 30 days post-procedure:

- ABI/TBI, resting
- Rutherford Classification
- Anti-platelet/Anti-coagulant therapy assessment
- Adverse Events
- Duplex Ultrasound

The following data are required and will be collected at 12, 24 and 36 months post-procedure:

- ABI/TBI, resting
- Rutherford Classification
- Anti-platelet/Anti-coagulant therapy assessment
- Adverse Events

CONFIDENTIAL INFORMATION

MD133246 Protocol Template

Revision#: 1

Doc Type: GC

- X-ray
- Duplex Ultrasound

The following data is required and will be collected at any Unscheduled Study-Related Visit or

- ABI/TBI, resting
- Rutherford Classification
- Anti-platelet/Anti-coagulant therapy assessment
- Angiography, if indicated
- Adverse Events
- Duplex Ultrasound, if indicated

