10.1. Primary Endpoint Analysis

10.1.1. Primary Effectiveness

The primary effectiveness endpoint is Primary Patency at 12 months post-procedure. Primary patency will be estimated through 365 days along with a 95% confidence interval using Kaplan-Meier analysis. Equivalent analysis will be performed with regards to the primary patency partitioning the data by lesion length (< 230 mm and \geq 230mm). All results will be compared to that obtained in the RELINE study.

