5.4 Primary Endpoints

5.4.1 Primary Effectiveness - Primary Patency at 12 Months Post-procedure

Both the ITT and PP populations will be used with the following decision rules for calculating the primary patency at 12 Months post-procedure.

CONFIDENTIAL INFORMATION

MD133254 Statistical Analysis Plan Template
Revision#: 1
Doc Type: GC

5.4.2 Primary Safety - Procedure or Device-related Serious Adverse Events Within 30 Days of the Index Procedure

Both the ITT and PP populations will be used with the following decision rules for calculating the serious adverse events within 30 days of the index procedure.

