5.5.2 Primary Patency

Both the ITT and PP populations will be used with the following decision rules for calculating the primary patency through Kaplan-Meier time to event analysis.

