6.2 Primary Endpoint

6.3 Verification Level for Statistical Output

7 Data Sets, Tables, Figures, and Listings

At a minimum, the following set of Tables, Figures, and Listings will be produced for the report. Unless specified, the populations for all tables are all of the “Enrolled Subjects”.

CONFIDENTIAL INFORMATION

MD133254 Statistical Analysis Plan Template
Revision#: 1
Doc Type: GC

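### Does the either/or in the definition of primary patency let a subject with PSVR above 2.5 count as patent?

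*Protocol*

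**What the plan says.** Protocol 3.2.1 defines primary patency as patent flow through the device that "requires either a PSVR measurement ≤ 2.5 or patent flow indicated by the Core Lab", with no repeat intervention. Protocol 10.2.2, SAP 2.3 and SAP 2.5.2 carry the same either/or. The general term has no velocity threshold: "Patency: blood flow through the study device".

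The definition sets the primary effectiveness endpoint at 12 months. Protocol 3.2.2 says of it: "This will be estimated through 365 days along with a 95% confidence interval using Kaplan-Meier analysis". It also sets the secondary primary-patency estimates at 30 days and at 12, 24 and 36 months. Under Protocol 10.1.1 the 12-month analysis is repeated for lesions below 230 mm and for those of 230 mm or more, and "All results will be compared to that obtained in the RELINE study".

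Duplex ultrasound is among the required assessments at 30 days ("The following data are required and will be collected at 30 days post-procedure", Protocol 5.7) and at 12, 24 and 36 months. Footnote 3 to Table 3 in Protocol 5.1 sends this imaging to the Core Lab.

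The SAP adds an operational layer. Section 5.4.1 says both analysis populations will be used "with the following decision rules for calculating the primary patency at 12 Months post-procedure", and section 5.5.2 says the same "with the following decision rules for calculating the primary patency through Kaplan-Meier time to event analysis". The rules themselves do not appear in the public text. Nor does anything under the SAP heading "6.2 Primary Endpoint".

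**The concern.** An either/or is satisfied when one limb is true. If the Core Lab limb means no more than visible flow, a restenosed device that is not occluded meets it whatever its velocity ratio. PSVR above 2.5 would then be a failure only when the Core Lab also declined to indicate patent flow, and the cut-off would do little work.

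No visible text ranks the two limbs, confines the Core Lab limb to scans without an evaluable PSVR, or defines patent flow. The possible error also runs one way. Compared with a rule in which an evaluable PSVR decides, the either/or can only leave reported patency unchanged or raise it. The study has a single arm, so no concurrent control would share a lenient classification, and the result is set beside an external study. At stake would be an overstated 12-month patency, overall and by lesion length.

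**Working it through.** The documents give no figure to reproduce here: the sample-size section is redacted and there is no stated count of conflicting reads. The check is therefore the logic of the definition, followed by the size of one reclassified subject.

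**Logic.** For a subject without repeat intervention, three possible rules give:

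| PSVR | Core Lab call | Either/or, literal | PSVR decides, Core Lab as fallback | Both required |
|---|---|---|---|---|
| ≤ 2.5 | patent | patent | patent | patent |
| ≤ 2.5 | not patent | patent | patent | lost |
| > 2.5 | patent | **patent** | **lost** | lost |
| > 2.5 | not patent | lost | lost | lost |
| not evaluable | patent | patent | patent | not assessable |
| not evaluable | not patent | lost | lost | lost |

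The literal rule and the fallback rule differ in the third row only. The issue exists only if the Core Lab, with the duplex study in hand, indicates patent flow in a device whose PSVR exceeds 2.5. The documents do not say whether it would ever do so.

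**Inputs for size.** From Protocol 3.1: N = 108 and at least 20 subjects with lesions of 230-270 mm, which leaves 108 − 20 = 88 others when that minimum is just met. From Table 4 in Protocol 5.7: the 12-month window is 365 ± 45 days, that is, days 320 to 410.

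**Step per reclassified subject, failure dated by day 365, no censoring (1/n):**

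- all subjects: 1/108 = 0.93 points
- long lesions at the minimum: 1/20 = 5.0 points
- the other 88: 1/88 = 1.14 points

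**Timing.** A failure dated after day 365 does not move the 365-day estimate. If failures are dated at the scan and 12-month scans are spread evenly over the window (both assumptions), the share dated by day 365 is (365 − 320)/(410 − 320) = 0.5, and the average step is 0.5 × 0.93 = 0.46 points. The 30-day scan falls on days 23 to 37, so a failure found there always counts.

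**Censoring.** Suppose 20% are censored before the 12-month scan, independently of failure (assumption). The Kaplan-Meier step is the survival estimate divided by the number at risk. With failure fraction f this is about (1 − f)/[108 × (1 − f) × 0.8] = 1/86.4 = 1.16 points, whatever f is.

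**Scale.** The number of conflicting subjects, k, is not given. With k = 0, 3, 5 or 10 (assumed), k/108 is 0, 2.8, 4.6 or 9.3 points. The approximate 95% half-width at n = 108, 1.96 × √[p(1 − p)/108], is 5.7 points at an assumed patency of 90% and 9.2 points at 60%. The two are compared for scale only, since a classification shift is not sampling error. One or two such subjects would be small against the interval; ten would not.

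**Reading the words together.** If any visible flow met the Core Lab limb, the PSVR limb would be almost idle wherever a Core Lab read exists. If the Core Lab call stands in for a PSVR that cannot be evaluated, both limbs have a purpose. Assisted and secondary patency (Protocol 10.2.3 and 10.2.4) ask the Core Lab to confirm blood flow, whereas primary patency speaks of patent flow. That difference suggests, without proving it, that more than the mere presence of flow was meant.

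**The case for a change.** The strongest case for a change is that the definition is published in full and its connector is plain. That the text says primary patency requires one of the two limbs does not help: strictly this states a necessary condition, but the only others given are flow through the device and no repeat intervention, and the subject in question meets both. If the withheld SAP rules rank the criteria, the definition should match them; if they do not, the cut-off can be bypassed. Either way, the argument goes, one sentence in each document would settle it. Duplex studies are already scheduled and already go to the Core Lab.

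Part of this stands. The published sentence does not say which criterion governs in a conflict, it leaves patent flow undefined, and the literal reading can only favour the device.

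The rest does not carry. A short definition completed by decision rules in the SAP is a normal division of labour, and a definition that leaves ranking to those rules is not thereby wrong. Text withheld from the public version cannot be counted as absent from the plan. The proposed sentence would also do more than clarify. Ruling that PSVR above 2.5 overrides the Core Lab chooses one endpoint over another, when the Core Lab's judgement of the whole study may have been intended to count. If RELINE used the same either/or, the rewording would damage the comparison the plan calls for. It would also be a protocol amendment needing IRB/EC approval (Protocol 6.6), for an effect nobody has shown to exist.

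**Conclusion.** The literal reading is right, but it does not show that following the full plan gives a wrong result. This is a gap in detail that the announced decision rules may already close. If they do not, the analysts and the Core Lab can fill it sensibly by using the Core Lab call where PSVR cannot be evaluated. The wording is the same in all four places, so the documents do not contradict each other. The visible primary analysis is an estimate with a 95% confidence interval, with no visible test or performance goal that a reclassified subject could tip.

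The total effect is unknown and may be zero. Per affected subject with failure dated by day 365 it is 0.93 points overall before censoring, about 1.16 points for a 12-month scan if 20% are censored earlier (assumed), and 5.0 points in a long-lesion group of 20. The conclusion rests on two things the public text cannot settle: what the withheld SAP rules say, and how often the Core Lab would indicate patent flow with PSVR above 2.5. It would need to be revisited if those rules apply the either/or literally and such reads turn out to be common. No change to the plan is called for.
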